#### 17.4.2.4.1. Time Point Response

It is assumed that at each protocol-specified time point, a response assessment occurs. Table 17.5 provides a summary of the overall response status calculation at each time point for subjects who have measurable disease at baseline.

When subjects have non-measurable (therefore non-target) disease only, Table 17.6 is to be used.

Table 17.5: Overall Response: Subjects with Target (± Non-target) Disease

Time Point Response: Su	bjects with Target (± Non-target)	Disease			
Target Lesions	Non-target Lesions	New Lesions	Overall Response		
CR	CR	No	CR		
CR	Non-CR/Non-PD	No	PR		
CR	Not evaluated	No	PR		
PR	Non-PD or not all evaluated	No	PR		
SD	Non-PD or not all evaluated	No	SD		
Not all Evaluated	Non-PD	No	NE		
PD	Any	Yes or No	PD		
Any	PD	Yes or No	PD		
Any	Any	Yes	PD		

CR = complete response; NE = inevaluable; PD = progressive disease; PR = partial response; SD = stable disease.

Table 17.6: Overall Response: Subjects with Non-target Disease Only

Time Point Response: Subjects with No	on-target Disease Only	
Non-target Lesions	New Lesions	Overall Response
CR	No	CR
Non-CR/Non-PD	No	Non-CR/Non-PD
Not all evaluated	No	NE
Unequivocal PD	Yes or No	PD
Any	Yes	PD

CR = complete response; NE = inevaluable; PD = progressive disease.

## 17.4.2.4.2. Missing Assessments and Inevaluable Designation

When no imaging/measurement is performed at all at a particular time point, the subject is not evaluable (NE) at that time point. If only a subset of lesion measurements are made at an assessment, usually the case is also considered NE at that time point, unless a convincing argument can be made that the contribution of the individual missing lesion(s) would not change the assigned time point response. This would be most likely to happen in the case of PD. For example, if a subject had a baseline sum of 50 mm with 3 measured lesions and at F/U only

2 lesions were assessed, but those gave a sum of 80 mm, the subject will have achieved PD status, regardless of the contribution of the missing lesion.

#### 17.4.2.4.3. Best Overall Response: All Time Points

The best overall response is determined once all the data for the subject is known.

Best response determination in this study where confirmation of CR or PR IS NOT required: Best response in this study is defined as the best response across all time points (eg, a subject who has SD at first assessment, PR at second assessment, and PD on last assessment has a best overall response of PR). When SD is believed to be best response, it must also meet the protocol specified minimum time from baseline, 6 weeks ( $\pm$  1 week). If the minimum time is not met when SD is otherwise the best time point response, the subject's best response depends on the subsequent assessments.

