In patients with advanced/unresectable or metastatic breast cancer classified as triple-negative breast cancer (TNBC; HER2-negative/HR-negative) chemotherapy remains the mainstay of treatment. While many drugs, including taxanes, anthracyclines, capecitabine, eribulin, S-1, and irinotecan, have shown activity, no standard of care has been established. Despite the treatment options presented by these agents, the prognosis for TNBC remains poor, with an estimated median overall survival of 10 to 18 months and post-progression survival of 6 months after first-line therapy. There is still an unmet medical need in advanced TNBC with disease progression after chemotherapy.

Considering the unmet medical need in breast cancer described here, an urgent need for the development of new therapy for advanced/unresectable or metastatic breast cancer is justified.

Preliminary data from Study U31402-A-J101 in patients with human epidermal growth factor receptor 3 (HER3)-positive, advanced/unresectable or metastatic breast cancer (N=42, total), including 10 subjects with TNBC, showed a persistent U3-1402 antitumor effect with a confirmed ORR of 42.9%, a DCR of 90.5%, and a median (range) PFS of 8.3 (1.2, 16.8) months (median follow-up of 10.5 months).

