#### 1.2.3. Clinical Experience

This is a first-in-human study of U3-1402.

As of the 25 Aug 2018 data cut-off, 56 subjects had received U3-1402 as part of Study U31402-A-J101: 34 subjects in the Dose Escalation Part, 8 subjects in the Dose Finding Part, and 14 subjects in the Dose Expansion Part. At the time of the data cut-off, 41 subjects were receiving treatment, 13 subjects had discontinued treatment due to disease progression, 1 subject had discontinued treatment due to Grade 2 pneumonitis, and 1 subject had withdrawn consent.

Fifty-four (96.4%) of the 56 treated subjects had experienced at least 1 TEAE. All 54 subjects had also experienced at least 1 TEAE considered by the investigator as related to study drug. Among all treated subjects, the most frequent (>20%) TEAEs, all grades, regardless of causality

and noted in descending order of frequency, included nausea (47 subjects [83.9%]), decreased appetite (36 subjects [64.3%]), platelet count decreased (36 subjects [64.3%]), white blood cell count decreased (30 subjects [53.6%]), neutrophil count decreased (29 subjects [51.8%]), vomiting (25 subjects [44.6%]), aspartate aminotransferase (AST) increased (23 subjects [41.1%]), alanine aminotransferase (ALT) increased (22 subjects [39.3%]), anemia (19 subjects [33.9%]), stomatitis (17 subjects [30.4%]), alopecia (15 subjects [26.8%]), diarrhea (15 subjects [26.8%]), fatigue (12 subjects [21.4%]), and malaise (12 subjects [21.4%]).

Eighteen (32.1%) of the 56 treated subjects had developed treatment-emergent SAEs, including 12 subjects (21.4%) with study drug-related SAEs. The treatment-emergent SAEs, in descending order of frequency, included platelet count decreased (6 subjects [10.7%]); decreased appetite (3 subjects [5.4%]); and atelectasis, cellulitis, cholecystitis acute, dehydration, dyspnea, implant site infection, malaise, myalgia, pneumonia, pneumothorax, pseudomembranous colitis, thrombocytopenia, and urinary tract infection (1 subject [1.8%] each).

Additional data describing the clinical experience of U3-1402 are available in the current Investigator's Brochure.

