#### **6.4.2.** Tumor Assessment

Tumor assessments of the chest, abdomen, pelvis, and other areas where scans were performed at screening or where new disease is suspected should be performed every 6 weeks ( $\pm$  7 days) in the first 24 weeks after Day 1 of Cycle 1 and every 12 weeks ( $\pm$  7 days) thereafter. Tumor assessments should not be delayed by dose interruptions; they are timed relative to Cycle 1, Day 1 and should continue until PD or until a new anticancer therapy is started, whichever occurs first.

CT or MRI scans of the chest, abdomen, and pelvis are mandatory. The same methodology (CT or MRI) and scan acquisition techniques (including use or nonuse of IV contrast) that were used for the screening assessments should be used throughout the study for all assessments for each subject, unless prior approval is obtained from the Sponsor. Unscheduled tumor assessments may be conducted if progression is suspected. Tumor assessments should be performed per RECIST version 1.1 (Section 17.4).

A brain scan (CT of the brain with contrast or MRI of the brain pre- and post-gadolinium) should be performed at screening. During the treatment period, CT or MRI of the brain should be performed in subjects with baseline brain metastases or where clinically indicated, and within a target of 1 week (+ 1 week) after a subject achieves CR.

A bone scan should be performed at screening. In subjects whose body CT/MRI scans indicate that CR has been achieved, a bone scan (within a target of 1 week [+ 1 week]) will be required at confirmation of CR to exclude new bone metastases.

All images including CT and MRI must be submitted to the central imaging CRO selected by the Sponsor for independent tumor assessment.

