# 11.5. Sample Size Determination

The Dose Escalation Part of this study consists of mCRM with EWOC design with at least 3 DLT-evaluable subjects per dose level. Sample size has been determined by practical considerations and no formal statistical assessment has been performed for the Dose Escalation Part.

A total of approximately 12 subjects will be enrolled between Dose Escalation and Dose Finding for each of the Q3W Dosing Cohorts evaluated in Dose Finding. For the alternative dosing cohorts evaluated in Dose Finding, a total of approximately 12 subjects will be enrolled into each cohort. RDE(s) will be determined based on the risk and benefit assessment.

For the Dose Expansion Part, there are 4 planned expansion cohorts (HER3-high, HR-positive [6.4 mg/kg], HER3-high, HR-positive [4.8 mg/kg], HER3-low, HR-positive [6.4 mg/kg] and HER3-high, TNBC [6.4 mg/kg]):

• Approximately 60 eligible subjects with HER3-high, HER2-negative, HR-positive disease will be randomized into 1 of 2 cohorts: 4.8 mg/kg or 6.4 mg/kg.

- Subjects with HER3-low, HER2-negative, HR-positive breast cancer will not be randomized. Approximately 20 eligible subjects in this setting will be enrolled into a HER3-low, HR-positive (6.4 mg/kg) cohort.
- Subjects with HER3-high, TNBC will not be randomized. Approximately 30 eligible subjects in this setting will be enrolled into an HER3-high, TNBC (6.4 mg/kg) cohort.

A total of approximately 110 subjects will be enrolled into the Dose Expansion Part.

In HER3-high, HR-positive cohorts of the Dose Expansion Part, if target ORR is more than 10% (null hypothesis: ORR  $\le$ 0.10, alternative hypothesis: ORR  $\ge$ 0.10), then the probability of no response out of 30 subjects will be less than 5%. The probability that more than 6 responders out of 30 subjects (ORR  $\ge$ 20%) are observed will be less than 5% under the null hypothesis with ORR  $\le$ 0.10 but more than 80% under alternative hypothesis with ORR = 0.30.

In the HER3-low, HR-positive cohort of the Dose Expansion Part, if target ORR is more than 10% (null hypothesis: ORR  $\le$ 0.10, alternative hypothesis: ORR  $\ge$ 0.10), then the probability of no response out of 20 subjects will be less than 15%. The probability that more than 3 responders out of 20 subjects (ORR  $\ge$ 15.0%) are observed will be less than 15% under the null hypothesis with ORR  $\le$ 0.10 but more than 75% under alternative hypothesis with ORR = 0.25.

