#### 17.4.2.4. Evaluation of Best Overall Response

Best response in this study is defined as the best response across all time points (eg, a subject who has SD at first assessment, PR at second assessment, and PD on last assessment has a best overall response of SD). When SD is believed to be best response, it must also meet the protocol specified minimum time from baseline, 6 weeks ( $\pm$  7 days). If the minimum time is not met when SD is otherwise the best time point response, the subject's best response depends on the subsequent assessments. For example, a subject who has SD at first assessment, PD at second and does not meet minimum duration for SD, will have a best response of PD. The same subject lost to follow-up after the first SD assessment would be considered inevaluable.

The subject's best overall response assignment will depend on the findings of both target and non-target disease and will also take into consideration the appearance of new lesions.

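### The best-overall-response rule contradicts itself on whether a single-scan response counts, so the Dose Expansion ORR and the Section 11.5 error rates rest on an undefined responder

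*Combined protocol and SAP*

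**What the plan says.** Two sections of the RECIST appendix score the same worked example, SD at the first assessment, PR at the second and PD at the last, in opposite ways:

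- Section 17.4.2.4: "PR at second assessment, and PD on last assessment has a best overall response of SD".
- Section 17.4.2.4.3, introduced by "Best response determination in this study where confirmation of CR or PR IS NOT required": "PR at second assessment, and PD on last assessment has a best overall response of PR".

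The ORR definitions in Sections 2.3, 9 and 11.4.1 add the CR and PR rates and do not mention confirmation. Section 1.1 says that preliminary data from this same study, in 42 subjects, "showed a persistent U3-1402 antitumor effect with a confirmed ORR of 42.9" per cent.

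Evaluating efficacy is part of the primary objective of the Dose Expansion Part (Section 2.1.1.3). That part has no control arm; its only randomization is between two doses in the HER3-high, HR-positive cohorts. Section 11.5 attaches false-positive and power bounds to responder counts (for example "The probability that more than 6 responders out of 30 subjects") against reference rates of 10% (HR-positive cohorts) and 20% (TNBC). It gives no source for these rates and does not say whether they, or the counts, refer to confirmed responses.

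**The concern.** A subject with one PR scan followed by progression is a responder under one section and a non-responder under the other. With no control arm, nothing cancels that difference: it passes directly into ORR, and it decides who enters the duration-of-response and time-to-response summaries.

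The direction is certain. In the same subjects every confirmed responder is also an unconfirmed responder, so unconfirmed ORR equals or exceeds confirmed ORR. The size is not known. What is at stake is whether the bounds in Section 11.5 describe the endpoint that will be reported.

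**Working it through.** **1. The two scorings.** Both sections open with the same definition, best response across all time points. Only the result of the example differs. SD is the result expected if a PR must be confirmed; PR is the result if it need not be. They cannot both apply.

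**2. Reproducing Section 11.5.** More than 6, 3 and 9 responders means at least r = 7, 4 and 10. The formula is P(X ≥ r | n, p) = Σ C(n,k) p^k (1−p)^(n−k), summed over k = r to n.

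| Cohort | Rule | p0 | False positive (stated) | p1 | Power (stated) |
|---|---|---|---|---|---|
| HER3-high, HR+ | ≥7/30 | 0.10 | 2.6% (<5%) | 0.30 | 84.0% (>80%) |
| HER3-low, HR+ | ≥4/20 | 0.10 | 13.3% (<15%) | 0.25 | 77.5% (>75%) |
| HER3-high TNBC | ≥10/30 | 0.20 | 6.1% (<10%) | 0.40 | 82.4% (>80%) |

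The probabilities of no response also hold: 0.90^30 = 4.2% (<5%), 0.90^20 = 12.2% (<15%) and 0.80^30 = 0.1% (<5%).

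**3. If p0 is a confirmed rate but responses are counted unconfirmed.** Put p0 + d in the same formula. The excess d is an assumption, because the documents give no figure for it.

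| Cohort | d = 0 | +1 point | +2 points | +5 points | Limit |
|---|---|---|---|---|---|
| HER3-high, HR+ | 2.6% | 4.1% | 6.1% | 15.3% | 5% |
| HER3-low, HR+ | 13.3% | 17.1% | 21.3% | 35.2% | 15% |
| HER3-high TNBC | 6.1% | 8.1% | 10.4% | 19.7% | 10% |

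At +1 point only the 20-subject cohort exceeds its limit; at +2 points all three do. The limits are reached at unconfirmed rates of 11.5%, 10.5% and 21.8%. The share of counted responses that would then be unconfirmed is 1 − p0/rate, about 13%, 4% and 8%.

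**4. If p0 is already an unconfirmed rate.** Then d = 0 and no limit is broken.

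**5. If p1 is an unconfirmed rate and the count becomes confirmed.** Put p1 − d in the formula, with d again assumed. For d = 2 to 5 points, power falls to 78%–65%, 71%–59% and 76%–64%.

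**6. Can the scheduled scans confirm?** Section 6.4.2 has scans every 6 weeks (±7 days) to week 24, then every 12 weeks. The smallest gap is from day 42 + 7 = 49 to day 84 − 7 = 77, which is 28 days. A PR first seen at week 24 is rechecked at week 36 (day 252 ± 7, so 245–259), before the 9-month minimum follow-up (about day 274). A PR first seen at week 36 is rechecked only at week 48 (day 336 ± 7), after it.

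**The case against.** The strongest reply is that the rule is settled. Section 17.4.2.4.3 states it explicitly, and the opening definition in 17.4.2.4 points the same way, so the SD in its example may be a slip. That may be so, but the text still scores one subject two ways, and the study's own ORR has been reported as confirmed. A further reply is that Section 17.4 leaves details to the Independent Review Charter and Section 11.6 leaves efficacy definitions to the SAP. The text reviewed here contains no such further rule, so a confirmed-ORR row elsewhere cannot be excluded.

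It is also fair that all scans go to independent central review, and that the efficacy analysis is descriptive, with exact confidence intervals and no formal go/no-go test tied to the counts. Central reading reduces reader bias; it does not remove measurement error on a single scan.

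Three stronger readings are tempting but not supported:

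- **The bone scan proves a second response definition.** Section 6.4.2 says a bone scan "will be required at confirmation of CR to exclude new bone metastases". It is due within a target of 1 week (+1 week) and looks for new bone lesions by another modality. It is not repeat-scan confirmation and fits either rule.
- **The Expansion ORR is inflated and the Section 11.5 limits fail.** Only the direction relative to a confirmed ORR is known. The limits hold as written and fail only on the premise in step 3.
- **Confirmation would make Expansion comparable with 42.9%.** No such comparison is planned. The 42 subjects probably come from other parts: at the 25 Aug 2018 cutoff Section 1.2.3 counts "34 subjects in the Dose Escalation Part, 8 subjects in the Dose Finding Part, and 14 subjects in the Dose Expansion Part", and 34 + 8 = 42. That is an inference; if right, doses and populations differ too.

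**Conclusion.** The contradiction between 17.4.2.4 and 17.4.2.4.3 is established from the text and needs correction, because it decides who counts as a responder for an endpoint under the primary objective.

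The effect on error rates is conditional. It requires that the 10% and 20% rates be confirmed rates while responses are counted unconfirmed, and its size depends on the assumed excess. The margin is thin on that premise: about 1.5, 0.5 and 1.8 points of excess reach the three limits. On the opposite premise the false-positive bounds stand. Since Section 11.5 is silent, its operating characteristics cannot be tied to a defined endpoint until this is stated.

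**What to change.** 1. State one best-overall-response rule in Sections 17.4.2.4, 17.4.2.4.3 and 11.4.1, carry it into the SAP, and correct the example that does not match.
2. Make the headline ORR, with DOR and TTR, CR or PR confirmed at a later scan at least 4 weeks after first documentation. The scheduled scans serve. Keep unconfirmed ORR as a supportive row.
3. Say in Section 11.5 whether p0, p1 and the responder counts are confirmed, and restate the probabilities if any of them changes.

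No new procedures are needed; the cost is wording and one table row. There are three downsides:

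- The headline ORR may be slightly lower.
- A response first seen at the last scan before cutoff, such as week 36, stays unconfirmed unless the cutoff is extended as Section 11.1 allows.
- If p1 was an unconfirmed rate, power falls as in step 5 of the working, below the stated bounds, and Section 11.5 must say so.

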## 17.4.2.4.4. Special Notes on Response Assessment

When nodal disease is included in the sum of target lesions and the nodes decrease to "normal" size (<10 mm), they may still have a measurement reported on scans. This measurement should be recorded even though the nodes are normal in order not to overstate progression should it be based on increase in size of the nodes. As noted earlier, this means that subjects with CR may not have a total sum of "zero" on the eCRF.

Subjects with a global deterioration of health status requiring discontinuation of treatment without objective evidence of disease progression at that time should be reported as "symptomatic deterioration." Every effort should be made to document objective progression even after discontinuation of treatment. Symptomatic deterioration is not a descriptor of an objective response: it is a reason for stopping study therapy. The objective response status of such subjects is to be determined by evaluation of target and non-target disease.

For equivocal findings of progression (eg, very small and uncertain new lesions; cystic changes or necrosis in existing lesions), treatment may continue until the next scheduled assessment. If at the next scheduled assessment, progression is confirmed, the date of progression should be the earlier date when progression was suspected.

#### 17.4.2.5. Frequency of Tumor Re-evaluation

In this study, tumor measurement will be conducted every 6 weeks in the first 24 weeks after Day 1 of Cycle 1 and thereafter every 12 weeks while the subject remains on study until progression of disease, withdrawal of consent, death, or loss to F/U. Scan dates should not be adjusted or rescheduled due to dose delay of any type.

Baseline tumor assessments must be performed within 28 days of the first dose of study drug administration.

All efforts should be made to ensure consistency between the baseline measurements and all subsequent measurements in reference to utilization of scanning method, equipment, technique (including slice thickness and field of view), and radiographic interpreter.

The radiographic evaluation must include CT or MRI scanning of the brain, chest, abdomen, and pelvis at screening period. Any additional suspected sites of disease should also be imaged.

Every effort should be made to use the same assessment modality for all assessments for each subject. However, if there is no brain metastasis at the time of screening, CT or MRI should only be done when symptoms associated with brain metastasis occur during study period. If no clinical symptoms are observed, brain CT or MRI is not mandatory during study period. All evaluations should meet the standard of care for imaging of lesions in the respective organ(s) and should conform to the image acquisition guidelines according to institutional standards.

All target and non-target sites are evaluated at each time point of tumor assessment.

#### 17.5. New York Heart Association Functional Classification

Class	Functional Capacity
I	No limitation of physical activity. Ordinary physical activity does not cause undue fatigue, palpitation, dyspnea (shortness of breath).
II	Slight limitation of physical activity. They are comfortable at rest. Ordinary physical activity results in fatigue, palpitation, dyspnea (shortness of breath).
III	Marked limitation of physical activity. Comfortable at rest. Less than ordinary activity causes fatigue, palpitation, or dyspnea.
IV	Unable to carry on any physical activity without discomfort. Symptoms of heart failure at rest. If any physical activity is undertaken, discomfort increases.

Source: https://www.heart.org/HEARTORG/Conditions/HeartFailure/AboutHeartFailure/Classes-of-Heart-Failure UCM 306328 Article.jsp (Updated: Apr 23, 2014)

## 17.6. Electronic Data Capture System

The EDC system used for completing eCRF in this study is shown below.

Name of EDC system	Medidata Rave®
EDC system developer	Medidata Solutions Inc.
Entry method	Web-based data entry
Input terminal	Desktop/laptop computer at the study site
Incompatible operating systems	None
Recommended browsers	The Medidata Rave® supports any browser which is HTML 5 and CSS2 compliant. Browsers must have JavaScript enabled.
Screen Resolution	The minimum screen resolution required to properly display Medidata Rave applications is $1024 \times 764$ .
Connection Speed	128kbps is the minimum connection speed recommended for using Medidata Rave.
Other	Adobe Flash Player: ver. 10 or above is required.

